---

## **GLOSSARY OF ABBREVIATIONS**

BASEC	Business Administration System for Ethical Committees
CRF	Case report form
FOPH	Federal Office of Public Health
HRA	Human Research Act
HRO	Ordinance on Human
WD	Wearable device

# 1 BACKGROUND AND PROJECT RATIONALE

Pediatric patients with cancer and chemotherapy-induced neutropenia are at great risk to develop severe and potentially life threatening infections. Initially, fever is often the only clinical detectable sign of such an infection. Therefore, fever in neutropenia is treated as an emergency, including hospitalization, start of intravenous empirical broad-spectrum antibiotics and close monitoring.

Several clinical decision rules have been established to distinguish between severe and less severe infections, based on the patient's history, clinical appearance and laboratory signs [4, 5], but with the exception of fever, vital signs are hardly explored. Delay of diagnosis and treatment can result in increased mortality [6], more intensive treatment [7] and more adverse events [8]. Time from hospital admission to antibiotics has been shown to influence clinical outcomes [8]. Wearable devices (WD) are already frequently used by athletes to monitor their activities and vital signs. Those devices are becoming smaller, more powerful and sophisticated and allow continuous recording of health data nearly everywhere and under any condition. Also in medical settings, WD are increasingly used for continuous measurements of patients' health data [9, 10]. Non-invasive on-skin wearable monitoring devices offer a broad set of health data that is recorded continuously [11].

It is hypothesized that continuous health data monitoring will provide more detailed information, and an more exact representation of the patient's health status than discrete measurements. Specifically it has been shown, that infections trigger changes of vital-signs very early in their course. For example heart-rate variability has been identified to change before clinical symptoms are detectable in neonates with sepsis [12] and in adults who underwent bone marrow transplant [13, 14]. Using a WD therefore opens the possibility to identify health data patterns that might be used as an additional diagnostic tool or a tool predicting imminent fever or infection in the near future. This may lead to earlier diagnosis and shorter time to antibiotics in patients at high risk for severe infection and the distinction from patients at lower risk.

## 1.1 Clinical Evidence to Date

Continuous monitoring with wrist-worn WDs has been shown to be possible for heart rate (Fitbit Charge HR©) [15] and physical activity (GENEActiv accelerometer) [16, 17] in healthy children. Several studies have assessed physical activity in pediatric patients undergoing chemotherapy with WDs worn on the ankle (StepWatch 3™ Activity Monitor) [18], waist (MTI Actigraph accelerometer) [19]; (Actical activity monitor) [20] or clothes (FitBit©) [21]. But no study has proven feasibility of continuous monitoring of other health data or vital signs with any WD in pediatric patients undergoing chemotherapy for cancer (search in PubMed, using (Accelerometer OR Wearable Electronic Devices/ OR wearable OR sensor OR tracker\*) AND (child OR children OR pediatric OR paediatric) AND (cancer/ OR cancer OR oncology), performed on June 20, 2019). It is not known if children tolerate a WD worn on the upper arm or thigh and if data quality sustains. Neither is it known if parents and patients can and are willing to handle a device in outpatient settings.

We know of a currently ongoing pilot study in pediatric inpatients aged 4 to 16 years with perforated appendicitis, osteomyelitis or septic arthritis, investigating the feasibility of continuous vital signs assessment with the Everion® at the University of Basel Children's Hospital (BASEC ID 2018-01926). In contrast to the present study, the Basel study excludes outpatients and patients below 4 years of age. Besides, the setting for children and adolescents undergoing chemotherapy for cancer is not comparable to patients receiving antibiotics for infections.

Additionally Everion® is currently investigated as one of five devices in an ongoing study trying to assess changes in physiological signals before and during seizures in children with epilepsy (NCT03745118).

## **2 PROJECT OBJECTIVES AND DESIGN**

### **2.1 Primary objective**

To assess the feasibility of continuous monitoring of heart rate in pediatric patients undergoing chemotherapy for cancer using the WD.

### **2.2 Secondary objectives**

Secondary objectives are related to:

- A. Further feasibility aspects
- B. Comparison of continuously recorded data with results of discrete measurements performed for clinical routine care
- C. Exploration for specific patterns in continuously recorded data before and during episodes of fever and infection

### **2.3 Choice of WD**

The WD investigated in this study is the Everion® by Biovotion, Zurich, Switzerland. To continuously monitor health data in children, a light and easy wearable device is needed, that does not hamper the child in any way during daily activities. The handling should be easy for the patients and/or parents to minimize the additional burden during the intensive treatment phases of chemotherapy. The Everion® is light (approximately 40g), without buttons and cables, and can be worn with an elastic band. Once the band is put on, the patient cannot tighten the band any further, as the size can only be adjusted by choosing the appropriate band size. This is more secure than an adjustable band for young children. As it is not known yet how to interpret the recorded data, it is necessary that the patients, parents and treating personnel do not have direct access to the data, as there is a risk for misinterpretation. In contrast to other WD, as smart-watches, the recorded data is not displayed on this WD. The Everion® is designed to measure with medical grade quality and provides a quality indicator for all calculated signals. It is CE-certified (CE 0123), medical device class IIa and FDA 510(k) exempt listed. Regulatory information: CE0123 ; MD Directive 93/42/EEC; RoHS Ro2011/65EU; Radioequipment Directive 2014/53/EU; Low Voltage Directive 2006/95/EC; WEE 2012/19/EU; EMC 2014/30 EU. One WD will be used for several patients, the WD is disinfected between different patients. For each patient a new elastic band will be used.

### **2.4 Signals and scores collected**

Everion® generates signals as vital signs or scores at a frequency of one per second. For this study aggregates will be used. Aggregates are filtered or averaged versions of signals and will be calculated every minute. Aggregates are calculated as quality-weighted average considering all signals whose quality is >50 and then weights each signal by the quality-30. The associated quality score is the average of all quality values >50, if more than 10% of quality values are >50, else it is the average of all quality values <50. For signals without quality scores aggregates are calculated as median value for all signals in the aggregation period of three minutes.

Description of Aggregates	unit	range	ID	Quality Score	name	ID
Signals comparable with discrete measurements						
S.1 HEART RATE	bpm	30-240	6	Q.1	HEART RATE QUALITY	68
S.2 OXYGEN SATURATION	%	60-100	7	Q.2	OXYGEN SATURATION QUALITY	69
S.3 RESPIRATION RATE	bps	2-60	12	Q.3	RESPIRATION RATE QUALITY	75
S.4 CTEMP (Core temperature)	°C	21-46	15	Q.4	CTEMP QUALITY	76
S.5 TEMPERATURE OBJECT (skin temperature)	°C	-10-40	118	-	-	-
Signals for general performance						
S.6 HEART RATE VARIABILITY	ms	2-140	11	Q.6	HEART RATE VARIABILITY QUALITY	74
S.7 PERFUSION INDEX	-	0-5	8	Q.7	PERFUSION INDEX QUALITY	133
S.8 HEALTH SCORE	-	0-100	22	-	-	-
S.9 GSR (Galvanic skin response)	kOhm	0-5	21	-	-	-

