### Quality Scores

Q.1 to Q.4 and Q.6: Quality scores for Signals S.1 to S.4 and S.6 [0 to 100; ≥50 indicates at least acceptable quality]

Q.7 Quality score for Signal S.7, perfusion of the skin [0 to 5.2; Higher values indicate better perfusion leading to better overall quality measurements; no limit defined for acceptable quality]

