### A. Secondary feasibility-related outcomes:

A1) At least acceptable quality scores (Q.2 to Q.4 and Q.6/7) of further signals (S.2 to S.4 and S.6/7 (see 2.3) during a cumulative duration of ≥18/24h per day (midnight to midnight), during ≥7 consecutive days within the 14 days of study duration (binary outcomes, measured once).

A2) Cumulative length of time with at least acceptable quality scores Q.1 to Q.4 and Q.6/7 (see 2.3) per study day (continuous outcomes, measured daily).

A4) Primary outcome and secondary outcomes A1 and A2 by skin type according to the Fitzpatrick scale [22] (Appendix 1).

A4) Primary outcome and secondary outcomes A1 and A2 by activity reported by parents and patients if applicable.

A5) Proportion of patients and parents indicating that continuous monitoring with the WD is acceptable per day and per entire study duration (binary outcome, measured daily plus once).

A6) Reasons not to wear the device as reported by parents and by patients if applicable (categorical outcome, measured daily).

A7) Side effects reported by parents and patients, if applicable (categorical outcome, measured daily)

A8) Effort (cumulative number and duration of contacts) per study day for the investigators (continuous outcomes, measured daily).

B) Secondary comparison-related outcomes:

B1) Difference between discrete measurements performed for clinical routine cares of heart rate and the mean of continuously measured signal S.1 (heart rate) within +/-10min at times of the discrete measurement (continuous outcomes, measured potentially multiple times).

B2) Like B1, for percutaneously measured blood oxygenation and signal S.2 (Oxygen Saturation).

B3) Like B1, for respiration rate and signal S.3 (respiration rate).

B4) Like B1, for ear temperature and signal S.4 (core temperature).

B5) Like B1, for ear temperature and signal S.5 (skin temperature).

C) Secondary outcomes for the exploration of specific patterns

C1) Exploration of potential changes in or specific patterns of the measured signals S.1 to S.9 and quality scores Q.1 to Q.6, within 48 hours before and after clinical diagnosis of fever (ear temperature of  $\geq 39.0^{\circ}\text{C}$ , or  $\geq 38.5^{\circ}\text{C}$  if fever is declared for clinical reasons) with or without neutropenia and microbiologically or clinically defined infections, if applicable.

C2) Like C1) for further signals collected with the WD.

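### The quality-weighted aggregation rule in section 2.4 cannot apply to the perfusion index S.7, because its score Q.7 runs only from 0 to 5.2, and no other rule for S.7 is stated

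*Combined protocol and SAP*

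**What the plan says.** Section 2.4 (Signals and scores collected) states that the device produces one value per second, and then: "For this study aggregates will be used". It gives two derivation rules.

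- For signals that have a quality score: "Aggregates are calculated as quality-weighted average considering all signals whose quality is >50 and then weights each signal by the quality-30". The score that goes with the aggregate follows a parallel rule: "The associated quality score is the average of all quality values >50, if more than 10% of quality values are >50". Otherwise it is the average of the values below 50.
- For the rest: "For signals without quality scores aggregates are calculated as median value for all signals in the aggregation period of three minutes".

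The table in the same section shows which signals have a score. S.5, S.8 and S.9 have none. S.7, the perfusion index, is paired with Q.7, "PERFUSION INDEX QUALITY" (ID 133).

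The Quality Scores list after the table puts Q.1 to Q.4 and Q.6 on a 0 to 100 scale, with 50 or more counted as acceptable. Q.7 is on a different scale: "Q.7 Quality score for Signal S.7, perfusion of the skin [0 to 5.2; Higher values indicate better perfusion". No acceptability limit is set for it.

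Outcome C1, in section 2.4 (Primary and secondary endpoints), explores "specific patterns of the measured signals S.1 to S.9 and quality scores Q.1 to Q.6" in the 48 hours before and after a diagnosis of fever. S.7 is therefore a planned input.

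**The concern.** The table places S.7 under the quality-weighted rule, and the filter in that rule lies far above the top of the Q.7 scale. The median rule is closed to S.7 because S.7 has a score. Neither written rule therefore gives an S.7 value, yet C1 needs one.

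What is at stake is reproducibility and possibly one exploratory signal. An analyst who works from the text must either report S.7 as missing or devise an undocumented rule once the data are in hand.

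This is separate from the fact that A1 and A2 refer to acceptable Q.7 values although no limit is defined. Setting a limit there, or dropping Q.7 from those outcomes, would still leave S.7 without a stated derivation.

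**Working it through.** The plan gives no figure of its own to reproduce. The check applies the written rule to the stated ranges.

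**Inputs** (all from section 2.4, Signals and scores collected, the Quality Scores list after it, and outcome C1)

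- Filter: quality q > 50. Weight: q − 30.
- Range of Q.7: 0 to 5.2. Range of Q.1 to Q.4 and Q.6: 0 to 100.
- Aggregates are calculated every minute, and the median rule names a three-minute period.
- Study period 14 days. C1 window 48 h before plus 48 h after, or 96 h.

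**Step 1: the S.7 value.** The rule is

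aggregate = Σ v(q − 30) / Σ (q − 30), summed over readings with q > 50.

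The largest possible Q.7 is 5.2, and 5.2 < 50. The set of readings kept is always empty, so the aggregate is undefined. This needs no assumption about how Q.7 is distributed.

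**Step 2: the count on a literal reading.** Per day there are 24 × 60 = 1,440 one-minute aggregates, so 14 × 1,440 = 20,160 per patient and 96 × 60 = 5,760 per C1 window. None has an S.7 value. Coding the rule and running it on simulated Q.7 values over 0 to 5.2 gave no S.7 value in 20,160 of 20,160 windows, with 60 and with 180 readings per window. A control window with a 0 to 100 score gave an ordinary aggregate. The simulation only confirms Step 1.

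**Step 3: the Q.7 score.** The share of Q.7 values above 50 is 0%, which is not more than 10%. The second branch applies, the mean of values below 50, and here that is the mean of all Q.7 values. A run at the maximum returned 5.2. Q.7 is thus still available at aggregate level; only the S.7 value is missing.

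**Step 4: would removing the filter be enough?** The weights would run from 0 − 30 = −30 to 5.2 − 30 = −24.8. In a normalised average the minus signs cancel, but the worst-perfused readings would count 30 / 24.8 = 1.21 times as much as the best. The effect is modest and in the wrong direction, since higher Q.7 means better perfusion. The weights, like the filter, are built for a 0 to 100 scale.

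**Step 5: is there a rule elsewhere?** Section 4.1 says only that exploratory methods will be adapted to the data type. That concerns analysis, not the derivation of a signal. No other section gives an S.7 rule.

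**The case against.** The strongest reply is that this is a gap in wording and not a loss of data. A reader might infer from Step 2 that S.7 will be empty for every patient and that perfusion drops out of the exploration of fever and infection. The documents do not support that, for three reasons.

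- The table in section 2.4 presents its rows as aggregates and lists S.7 with ID 8 and range 0 to 5, so the authors expect an S.7 aggregate to exist.
- Section 2.4 does not say who computes the aggregates. Section 7.2 has the investigators download the data through the manufacturer's interface. S.7 may arrive already aggregated by a rule that the protocol does not give.
- Q.7, itself described as skin perfusion, is still produced. C1 lists quality scores only up to Q.6, but C2 extends the exploration to further device signals, which arguably leaves room for Q.7.

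The reply also notes that C1 is exploratory, carries no test or decision, and that an empty column would be seen at once, so no silent bias would follow. A move to the median rule also raises the question of its three-minute period beside one-minute aggregates.

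All of this stands as to consequence and weight. It does not rescue the text. The written rule fails when applied to S.7, and if the device uses another rule, the protocol describes the wrong one for that signal.

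**Conclusion.** The point holds as a specification error of minor severity. The filter, the Q.7 range, the restriction on the median rule and the inclusion of S.7 in C1 are all in the text, and together they leave S.7 without a workable derivation.

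The practical size depends on a fact that the documents do not settle:

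- If the study team derives aggregates from per-second data by the written rule, S.7 has no value in any minute.
- If S.7 is delivered already aggregated by another rule, no data are lost and only the description needs correcting.

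In either case one of nine signals in one exploratory outcome is affected. The primary outcome rests on Q.1, which is scored 0 to 100, and is untouched.

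**What to change.** In section 2.4 (Signals and scores collected), limit the quality-weighted rule to the signals scored 0 to 100, that is S.1 to S.4 and S.6, and add a sentence giving the rule for S.7:

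- If S.7 arrives already aggregated, state the manufacturer's actual rule.
- Otherwise, use the median of the per-second S.7 values and name the aggregation window, since the section mentions both one minute and three minutes.

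Report Q.7 descriptively alongside S.7.

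The cost is about one sentence, plus one line of derivation code if the team computes the aggregates itself. No new data or procedures are needed. The downside of the median is that S.7 would not be filtered by quality, so some minutes may include readings with poor contact; the descriptive Q.7 helps a reader to judge this.

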#### 3.1.2 Study period

There will be no additional examinations or procedures performed for this study, specifically no additional discrete measurements of vital signs will be undertaken unless the clinically indicated measurements. Daily activities and temperature measurements if taken during outpatient stay will be recorded on case report forms (CRF) by parents and/or by patients. Questionnaires will be used for the assessment of WD acceptance, side effects and reasons not to wear the device. Parents, patients and members of the treating staff will not be able to access the continuously measured data, in order to avoid any influence on clinical decision making due to these data.

During the measurement period of 14 days no extra visits are planned. During the whole study period, one of the investigators will do a daily data-check, to see if data is recorded properly or not. If no data is recorded or if there are signs for reduced data quality, the parents and/or patients will be contacted by phone. Possible reasons for non-recording or reduced data quality

will be discussed on the phone and instructions will be given to parents and/or patients. During hospital visits calls may be replaced by on ward visits.

Parents and/or patients can contact the study site by phone any time by calling the pediatric oncology ward (24h emergency number) or outpatient ward and ask for assistance with the WD. Investigators are allowed to additionally check data recording, when contacted by parents or patients. Date, number, duration and reason of phone contacts and visits will be noted.

During the study period, parents and/or patients will be in charge for battery charging (approx. 2 hours each day) and data upload via mobile phone app. Parents and/or patients will fill out a CRF daily and note time of charging, connection to the mobile phone, reasons for not wearing the WD, any side effects, activities and temperature measurements, if applicable.

During hospitalization treating staff will perform discrete measurements as clinically indicated and note them in the patient chart. Parents and/or patients will continue to fill out the CRF daily. The charts will be assessed by the investigators to match the recorded data with the data from the WD.

The study period ends regularly for each patient after the planned period of 14 days, in case of intensive care unit admission or at the day of death from any cause, unrelated to the study.

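### Skin temperature (S.5) has no quality or wear screen in B5 or C1, so any readings output while the device is off the skin would count as patient data

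*Combined protocol and SAP*

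**What the plan says.** Section 2.4 (Signals and scores collected) has two aggregation rules. For signals with a quality score: "Aggregates are calculated as quality-weighted average considering all signals whose quality is >50 and then weights each signal by the quality-30". For the rest: "For signals without quality scores aggregates are calculated as median value for all signals in the aggregation period of three minutes". The table there shows no quality score for S.5 (skin temperature), S.8 (health score) and S.9 (galvanic skin response), and gives S.5 a range of -10 to 40 °C. The Quality Scores paragraph gives Q.7, the score for S.7, a scale of 0 to 5.2 and no acceptability limit.

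In section 2.4 (Primary and secondary endpoints), B5 compares ear temperature with the mean of S.5 within ±10 min. C1 covers the 48 h either side of a fever diagnosis and is described as "Exploration of potential changes in or specific patterns of the measured signals S.1 to S.9 and quality scores Q.1 to Q.6".

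Section 3.1.2 makes families responsible for "battery charging (approx. 2 hours each day" and has them note on a daily CRF when the device was charged and why it was not worn. Section 3.4 keeps non-wearers in the study. Section 4.1 leaves the exploratory methods open, and section 4.2 rules out imputation.

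**The concern.** The plan expects the device to be off the skin every day for charging, and at other times when the child will not wear it. For S.5 it takes the median of whatever was recorded, with no test of whether the device was on the patient. A median resists a few stray readings. It does not resist a removal that fills the whole three-minute period.

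In B5, an off-skin window would appear as a large disagreement between the device and the ear thermometer, although it says nothing about how well the sensor measures skin temperature. In C1 the risk is a false pattern. If a sick child is more likely to take the device off around the onset of fever, the resulting fall in S.5 could be read as a change that precedes or accompanies fever, which is what secondary objective C looks for.

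**Working it through.** **Is there a screen elsewhere?** The plan has no figure of its own to reproduce, so the first check is textual.

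- Aggregation (2.4, Signals): the >50 rule needs a quality score on the 0 to 100 scale. S.1 to S.4 and S.6 have one. S.5, S.8 and S.9 have none. Q.7 stops at 5.2, so a >50 rule cannot work for S.7.
- Range: 20 to 26 °C lies inside -10 to 40 °C, so a range check would not reject room temperature.
- Endpoints (2.4): B5 and C1 carry no wear, charging or quality condition.
- CRF (3.1.2): charging has a time; other non-wear has only a reason. No section uses either to remove data.
- Sections 4.1 and 4.2: no rule sets off-skin readings to missing.

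**How large could it be for S.5?** From the documents: 2 h of charging per day, a ±10 min window, and 48 h either side of fever. Assumed, not in the documents: skin at 33-35 °C, surroundings at 20-26 °C, S.5 recorded off the skin and during charging, one charging block per day, and ear-temperature times unrelated to it.

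1. Skin minus surroundings: smallest 33 - 26 = 7 °C, largest 35 - 20 = 15 °C.
2. One B5 window has 21 one-minute aggregates. With k of them off the skin, the S.5 mean falls by k/21 × (7 to 15):
   - k = 5: 1.7 to 3.6 °C
   - k = 10: 3.3 to 7.1 °C
   - k = 21: 7 to 15 °C
3. Share of windows that touch a 2 h block: (120 + 20)/1440 = 9.7%. Share wholly inside it: (120 - 20)/1440 = 6.9%.
4. The average off-skin share of a window is 2/24 = 8.3%. The mean B5 difference therefore moves by 0.0833 × 7 = 0.6 °C to 0.0833 × 15 = 1.25 °C.
5. If the device does not record while charging, the shift from charging is zero.
6. An extreme case: a day can meet the primary criterion of 18 h and still lack acceptable heart-rate signal for 6 h. If all 6 h were off the skin and recorded, and ear-temperature times were unrelated to them, the shift would be 6/24 × 7 = 1.75 °C to 6/24 × 15 = 3.75 °C. Poor signal is not the same as removal, so this is a scenario and not an estimate.
7. C1: 96 h × 60 = 5,760 minutes, of which charging takes 5,760 × 2/24 = 480.

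No such calculation is possible for S.7, S.8 or S.9, because the documents give no indication of what they would read off the skin.

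**The case against.** The strongest reply is that the mechanism is not documented. Nothing says that the device outputs S.5 off the skin or on the charger, and the temperatures above are assumed. This stands: the size is unknown and may be zero.

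A second reply is that the information already exists. Charging times are on the CRF, an investigator checks the data daily, and C1 looks at quality scores beside the signals, so a removal might be visible. This stands in part. The material is there, but no sentence commits to using it, B5 has no such cross-check, and non-wear other than charging has no recorded times.

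Third, these are descriptive secondary outcomes in a 20-patient pilot. That is correct and limits the importance of the point.

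Fourth, Q.1 measures heart-rate signal quality and not wear. If quality worsens with illness or movement, a Q.1 filter itself selects data around fever. This stands, and it is why the fix includes an analysis without that filter.

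A reader might infer more than the documents support:

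- That only S.5, S.8 and S.9 escape the >50 screen. S.7 does too.
- That the S.5 range proves off-skin recording. It shows only that room temperature would not be rejected as out of range.
- That the >50 rule removes unworn time for the other signals. The documents do not say how quality behaves off the skin.
- That health score or galvanic skin response would fall on removal. Nothing supports a direction.
- That section 2.3 contradicts the table by saying the device "provides a quality indicator for all calculated signals". Skin temperature may be a direct reading and not a calculated signal, and this background text drives no analysis.

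**Conclusion.** The gap in the analysis rules is real and is clearest for S.5 in B5 and C1: there is no quality score, no wear condition, and a range that lets room temperature through. Whether it does harm depends on one undocumented fact, namely whether S.5 is output off the skin. If it is, including during charging, and under the stated temperatures and timing, charging alone moves the mean B5 difference by about 0.6 to 1.25 °C; single windows wholly off the skin are wrong by 7 to 15 °C. For S.7, S.8 and S.9 in C1 the screen is equally absent, but the consequence cannot be judged. The primary outcome and the 15-of-20 feasibility claim rest on Q.1 and are untouched. This is a cheap improvement to secondary and exploratory outcomes, not a threat to the study's main conclusion.

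**What to change.** - In sections 2.4 and 4.1, state that S.5 in B5 and C1, and S.7 to S.9 in C1, are used only where Q.1 is ≥50 in every minute of the aggregation period. A same-minute check is not enough, because a three-minute median can still contain off-skin readings.
- Remove the charging times noted on the CRF.
- Add start and stop times of other non-wear to the CRF.
- Report the number of B5 pairs and C1 minutes excluded.
- Show the result with only charging times removed, and no Q.1 filter, as a sensitivity check.
- State whether the device outputs these signals off the skin and while charging. If it does not, saying so largely settles the point.

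The cost is a filter on data already downloaded, one more CRF entry for families, and a second set of summaries. Some worn minutes with a poor heart-rate signal will be lost, possibly more of them around fever; the sensitivity check is there to show whether that matters. The mask assumes that Q.1 falls below 50 off the skin, which the documents do not state, so the CRF times are needed as well.
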